**CONFIDENTIAL**

*This document is confidential. Do not disclose or use unless authorized.*

The Pharmacy Manual contains specific instructions for the preparation of the pembrolizumab infusion fluid and administration of infusion solution.

### **7.1.3 Trial Blinding/Masking**

This is an open-label trial; therefore, the Sponsor, investigator and subject will know the treatment administered.

### **7.1.4 Stopping Rules**

The study will be stopped if greater than 30% of patients discontinue pembrolizumab due to an adverse event or for any patient death related to toxicity.

## **7.2 Randomization or Treatment Allocation**

Subjects participating in this trial will be allocated to trial treatment by non-random assignment.

## **7.3 Stratification**

No stratification based on age, sex, or other characteristics will be used in this trial.

## **7.4 Concomitant Medications/Vaccinations (allowed & prohibited)**

Medications or vaccinations specifically prohibited in the exclusion criteria are not allowed during the ongoing trial. If there is a clinical indication for one of these or other medications or vaccinations specifically prohibited during the trial, discontinuation from trial therapy or vaccination may be required. The investigator should discuss any questions regarding this with the Merck Clinical team. The final decision on any supportive therapy or vaccination rests with the investigator and/or the subject's primary physician.

### **7.4.1 Acceptable Concomitant Medications**

All treatments that the investigator considers necessary for a subject's welfare may be administered at the discretion of the investigator in keeping with the community standards of medical care. All concomitant medication will be recorded on the case report form (CRF) including all prescription, over-the-counter (OTC), herbal supplements, and IV medications and fluids. If changes occur during the trial period, documentation of drug dosage, frequency, route, and date may also be included on the CRF.

All concomitant medications received within 28 days prior to study registration and 30 days after the last dose of trial treatment should be recorded. Concomitant medications administered after 30 days after the last dose of trial treatment should be recorded for SAEs and ECIs as defined in Section 11.0: Adverse Event Reporting Requirement.

---

*CONFIDENTIAL*

*This document is confidential. Do not disclose or use unless authorized.*

#### **7.4.2 Prohibited Concomitant Medications**

Subjects are prohibited from receiving the following therapies during the Screening and Treatment Phase (including retreatment for post-complete response relapse) of this trial:

- Antineoplastic systemic chemotherapy or biological therapy
- Immunotherapy not specified in this protocol
- Chemotherapy not specified in this protocol
- Investigational agents other than pembrolizumab
- Radiation therapy
  - Note: Radiation therapy to a symptomatic solitary lesion or to the brain may be allowed at the investigator's discretion.
- Live vaccines within 30 days prior to the first dose of trial treatment and while participating in the trial. Examples of live vaccines include, but are not limited to, the following: measles, mumps, rubella, varicella/zoster, yellow fever, rabies, BCG, and typhoid vaccine.
- Systemic glucocorticoids for any purpose other than to modulate symptoms from an event of clinical interest of suspected immunologic etiology. The use of physiologic doses of corticosteroids may be approved after consultation with the Sponsor.
- Intralesional or systemic antiviral treatment within 30 days prior to the first dose of trial treatment and while participating in the trial.

Subjects who, in the assessment by the treating investigator, require the use of any of the aforementioned treatments for clinical management should be removed from protocol treatment. Subjects may receive other medications that the treating investigator deems to be medically necessary.

The Exclusion Criteria describes other medications which are prohibited in this trial.

There are no prohibited therapies during the Post-Treatment Follow-up Phase.

#### **7.5 Rescue Medications & Supportive Care**

##### **7.5.1 Supportive Care Guidelines**

Subjects should receive appropriate supportive care measures as deemed necessary by the treating investigator. Suggested supportive care measures for the management of adverse events with potential immunologic etiology are outlined below and in greater detail in the ECI guidance document. Where appropriate, these guidelines include the use of oral or intravenous treatment with corticosteroids as well as additional anti-inflammatory agents if symptoms do not improve with administration of corticosteroids. Note that several courses of steroid tapering may be necessary as symptoms may worsen when the steroid dose is decreased. For each disorder, attempts should be made to rule out other causes such as metastatic disease or bacterial or viral

---

*CONFIDENTIAL*

*This document is confidential. Do not disclose or use unless authorized.*

infection, which might require additional supportive care. The treatment guidelines are intended to be applied when the investigator determines the events to be related to pembrolizumab.

Note: if after the evaluation the event is determined not to be related, the investigator is instructed to follow the ECI reporting guidance but does not need to follow the treatment guidance (as outlined in the ECI guidance document). Refer to Section 7.1.1 for dose modification.

It may be necessary to perform conditional procedures such as bronchoscopy, endoscopy, or skin photography as part of evaluation of the event. Suggested conditional procedures, as appropriate, can be found in the ECI guidance document.

- **Pneumonitis:**

- For **Grade 2 events**, treat with systemic corticosteroids. When symptoms improve to Grade 1 or less, steroid taper should be started and continued over no less than 4 weeks.
- For **Grade 3-4 events**, immediately treat with intravenous steroids. Administer additional anti-inflammatory measures, as needed.
- Add prophylactic antibiotics for opportunistic infections in the case of prolonged steroid administration.

- **Diarrhea/Colitis:**

Subjects should be carefully monitored for signs and symptoms of enterocolitis (such as diarrhea, abdominal pain, blood or mucus in stool, with or without fever) and of bowel perforation (such as peritoneal signs and ileus).

- All subjects who experience diarrhea/colitis should be advised to drink liberal quantities of clear fluids. If sufficient oral fluid intake is not feasible, fluid and electrolytes should be substituted via IV infusion. For Grade 2 or higher diarrhea, consider GI consultation and endoscopy to confirm or rule out colitis.
- For **Grade 2 diarrhea/colitis** that persists greater than 3 days, administer oral corticosteroids.
- For **Grade 3 or 4 diarrhea/colitis** that persists greater than 3 days, treat with intravenous steroids followed by high dose oral steroids.
- When symptoms improve to Grade 1 or less, steroid taper should be started and continued over no less than 4 weeks.

- **Type 1 diabetes mellitus (if new onset, including diabetic ketoacidosis [DKA]) or ≥ Grade 3 Hyperglycemia, if associated with ketosis (ketonuria) or metabolic acidosis (DKA)**

- For **T1DM** or **Grade 3-4 Hyperglycemia**
  - Insulin replacement therapy is recommended for Type I diabetes mellitus and for Grade 3-4 hyperglycemia associated with metabolic acidosis or ketonuria.
  - Evaluate patients with serum glucose and a metabolic panel, urine ketones, glycosylated hemoglobin, and C-peptide.

---

CONFIDENTIAL

*This document is confidential. Do not disclose or use unless authorized.*

- **Hypophysitis:**
  - For **Grade 2** events, treat with corticosteroids. When symptoms improve to Grade 1 or less, steroid taper should be started and continued over no less than 4 weeks. Replacement of appropriate hormones may be required as the steroid dose is tapered.
  - For **Grade 3-4** events, treat with an initial dose of IV corticosteroids followed by oral corticosteroids. When symptoms improve to Grade 1 or less, steroid taper should be started and continued over no less than 4 weeks. Replacement of appropriate hormones may be required as the steroid dose is tapered.
- **Hyperthyroidism or Hypothyroidism:**

Thyroid disorders can occur at any time during treatment. Monitor patients for changes in thyroid function (at the start of treatment, periodically during treatment, and as indicated based on clinical evaluation) and for clinical signs and symptoms of thyroid disorders.

  - **Grade 2** hyperthyroidism events (and **Grade 3-4** hypothyroidism):
    - In hyperthyroidism, non-selective beta-blockers (e.g. propranolol) are suggested as initial therapy.
    - In hypothyroidism, thyroid hormone replacement therapy, with levothyroxine or liothyroinine, is indicated per standard of care.
  - **Grade 3-4** hyperthyroidism
    - Treat with an initial dose of IV corticosteroid followed by oral corticosteroids. When symptoms improve to Grade 1 or less, steroid taper should be started and continued over no less than 4 weeks. Replacement of appropriate hormones may be required as the steroid dose is tapered.
- **Hepatic:**
  - For **Grade 2** events, monitor liver function tests more frequently until returned to baseline values (consider weekly).
    - Treat with IV or oral corticosteroids
  - For **Grade 3-4** events, treat with intravenous corticosteroids at least for 24 to 48 hours.
  - When symptoms improve to Grade 1 or less, a steroid taper should be started and continued over no less than 4 weeks.
- **Renal Failure or Nephritis:**
  - For **Grade 2** events, treat with corticosteroids.
  - For **Grade 3-4** events, treat with intravenous corticosteroids.
  - When symptoms improve to Grade 1 or less, steroid taper should be started and continued over no less than 4 weeks.

---

*CONFIDENTIAL*

*This document is confidential. Do not disclose or use unless authorized.*

- **Management of Infusion Reactions:** Signs and symptoms usually develop during or shortly after drug infusion and generally resolve completely within 24 hours of completion of infusion.

*Table 4* below shows treatment guidelines for subjects who experience an infusion reaction associated with administration of pembrolizumab (MK-3475).

*Table 4: Infusion Reaction Treatment Guidelines*

NCI CTCAE Grade	Treatment	Premedication at subsequent dosing
Grade 1 Mild reaction; infusion interruption not indicated; intervention not indicated	Increase monitoring of vital signs as medically indicated until the subject is deemed medically stable in the opinion of the investigator.	None
Grade 2 Requires infusion interruption but responds promptly to symptomatic treatment (e.g., antihistamines, NSAIDS, narcotics, IV fluids); prophylactic medications indicated for <=24 hrs	
Stop Infusion and monitor symptoms.                      Additional appropriate medical therapy may include but is not limited to:
 
 
IV fluids
 
Antihistamines
 
NSAIDS
 
Acetaminophen
 
Narcotics
 
 
Increase monitoring of vital signs as medically indicated until the subject is deemed medically stable in the opinion of the investigator.                      If symptoms resolve within one hour of stopping drug infusion, the infusion may be restarted at 50% of the original infusion rate (e.g., from 100 mL/hr to 50 mL/hr). Otherwise dosing will be held until symptoms resolve and the subject should be premedicated for the next scheduled dose.
 
Subjects who develop Grade 2 toxicity despite adequate premedication should be permanently discontinued from further trial treatment administration.
	
Subject may be premedicated 1.5h (<math>\pm</math> 30 minutes) prior to infusion of pembrolizumab (MK-3475) with:
 
 
Diphenhydramine 50 mg po (or equivalent dose of antihistamine).
 
Acetaminophen 500-1000 mg po (or equivalent dose of antipyretic).
 
 
Subsequent rate of infusions should be no more than 50% of rate at which reaction occurred.

Grades 3 or 4  Grade 3: Prolonged (i.e., not rapidly responsive to symptomatic medication and/or brief interruption of infusion); recurrence of symptoms following initial improvement; hospitalization indicated for other clinical sequelae (e.g., renal impairment, pulmonary infiltrates)  Grade 4: Life-threatening; pressor or ventilatory support indicated	
Stop Infusion.                      Additional appropriate medical therapy may include but is not limited to:
 
 
IV fluids
 
Antihistamines
 
NSAIDS
 
Acetaminophen
 
Narcotics
 
Oxygen
 
Pressors
 
Corticosteroids
 
Epinephrine
 
 
Increase monitoring of vital signs as medically indicated until the subject is deemed medically stable in the opinion of the investigator.                      Hospitalization may be indicated.
 
Subject is permanently discontinued from further trial treatment administration.
	No subsequent dosing
Appropriate resuscitation equipment should be available in the room and a physician readily available during the period of drug administration.		

*CONFIDENTIAL*

*This document is confidential. Do not disclose or use unless authorized.*

## **7.6 Diet/Activity/Other Considerations**

### **7.6.1 Diet**

Subjects should maintain a normal diet unless modifications are required to manage an AE such as diarrhea, nausea or vomiting.

### **7.6.2 Contraception**

Pembrolizumab may have adverse effects on a fetus in utero. Furthermore, it is not known if pembrolizumab has transient adverse effects on the composition of sperm. Non-pregnant, non-breast-feeding women may be enrolled if they are willing to use 2 methods of birth control or are considered highly unlikely to conceive. Highly unlikely to conceive is defined as 1) surgically sterilized, or 2) postmenopausal (a woman who is  $\geq 45$  years of age and has not had menses for greater than 1 year will be considered postmenopausal), or 3) not heterosexually active for the duration of the study. The two birth control methods can be either two barrier methods or a barrier method plus a hormonal method to prevent pregnancy. Subjects should start using birth control from study Visit 1 throughout the study period up to 120 days after the last dose of study therapy.

The following are considered adequate barrier methods of contraception: diaphragm, condom (by the partner), copper intrauterine device, sponge, or spermicide. Appropriate hormonal contraceptives will include any registered and marketed contraceptive agent that contains an estrogen and/or a progestational agent (including oral, subcutaneous, intrauterine, or intramuscular agents).

Subjects should be informed that taking the study medication may involve unknown risks to the fetus (unborn baby) if pregnancy were to occur during the study. In order to participate in the study they must adhere to the contraception requirement (described above) for the duration of the study and during the follow-up period defined in Section 11.5.6: Reporting of Pregnancy and Lactation to the Sponsor and to Merck. If there is any question that a subject will not reliably comply with the requirements for contraception, that subject should not be entered into the study.

### **7.6.3 Use in Pregnancy**

If a subject inadvertently becomes pregnant while on treatment with pembrolizumab, the subject will immediately be removed from the study treatment. The site will contact the subject at least monthly and document the subject's status until the pregnancy has been completed or terminated. The outcome of the pregnancy will be reported to the Coordinating Center and to Merck without delay; if the outcome is a serious adverse experience (e.g., death, abortion, congenital anomaly, or other disabling or life-threatening complication to the mother or newborn), the outcome must be reported within 24 hours to the Coordinating Center and within 2 working days to Merck.

The study investigator will make every effort to obtain permission to follow the outcome of the pregnancy and report the condition of the fetus or newborn to the Sponsor. If a male subject impregnates his female partner the study personnel at the site must be informed immediately and

---

*CONFIDENTIAL*

*This document is confidential. Do not disclose or use unless authorized.*

the pregnancy reported to the Coordinating Center and to Merck and followed as described above and in Section 11.5.6.

#### 7.6.4 Use in Nursing Women

It is unknown whether pembrolizumab is excreted in human milk. Since many drugs are excreted in human milk, and because of the potential for serious adverse reactions in the nursing infant, subjects who are breast-feeding are not eligible for enrollment.

### 7.7 Criteria for Removal from Protocol Treatment

Subjects may withdraw consent for protocol treatment and/or study itself at any time for any reason or be removed from the protocol treatment and/or study itself at the discretion of the investigator should any untoward effect occur. In addition, a subject may be withdrawn by the treating investigator or the Sponsor if enrollment into the trial is inappropriate, the trial plan is violated, or for administrative and/or other safety reasons. Specific details regarding discontinuation or withdrawal are provided in Section 10.1.4: Other Procedures.

Treatment may continue until one of the following criteria applies:

- The subject withdraws consent to treatment.
- Confirmed radiographic disease progression

*NOTE: A subject may be granted an exception to continue on treatment with confirmed radiographic progression if clinically stable or clinically improved*

- Unacceptable adverse experiences as described in Section 7.1.1
- Intercurrent illness that prevents further administration of treatment
- Investigator's decision to withdraw the subject
- The subject has a confirmed positive serum pregnancy test
- Noncompliance with trial treatment or procedure requirements
- The subject is lost to follow-up
- Completed 24 months of uninterrupted treatment with pembrolizumab or 35 administrations of study medication, whichever is later.

*NOTE: 24 months of study medication is calculated from the date of first dose. Subjects who stop pembrolizumab after 24 months may be eligible for up to one year of additional study treatment if they progress after stopping study treatment provided they meet the requirements detailed in Section 10.1.5.5*

- Treatment was held for 9 weeks for reasons other than complete response
- Administrative reasons

---

CONFIDENTIAL

*This document is confidential. Do not disclose or use unless authorized.*

Participants will be removed from the protocol therapy when any of these criteria apply. Participants removed from protocol therapy for unacceptable adverse event(s) will be followed until resolution or stabilization of the adverse event. Alternative care options will be discussed with the participant.

The reason for removal from protocol therapy, and the date the participant was removed, must be documented in the case report form (CRF). The research team also updates the relevant Off Treatment/Off Study information in OnCore; the Coordinating Center updates the relevant information for participating sites.

The End of Treatment and Follow-up visit procedures are listed in Section 9 (Protocol Flow Chart) and Section 10.1.5 (Visit Requirements). After the end of treatment, each subject will be followed for 30 days for adverse event monitoring (serious adverse events will be collected for 90 days after the end of treatment). Subjects who discontinue for reasons other than first progressive disease will have post-treatment follow-up for disease status until disease progression, initiating a non-study cancer treatment, withdrawing consent, becoming lost to follow-up, death, or 36 months post-study registration. After documented first disease progression each subject will be followed by telephone for overall survival until death, withdrawal of consent, or 36 months post-study registration, whichever occurs first.

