### 7.1.1.2 Dose Modification

Adverse events (both non-serious and serious) associated with pembrolizumab exposure may represent an immunologic etiology. These adverse events may occur shortly after the first dose or several months after the last dose of treatment. Pembrolizumab must be withheld for drug-related toxicities and severe or life-threatening AEs as per Table 3 below. See Section 7.5.1 and Events of Clinical Interest (ECI) Guidance Document (Appendix E) for supportive care guidelines, including use of corticosteroids.

*Table 3: Dose Modification Guidelines for Drug-Related Adverse Events*

Toxicity	Hold Treatment For Grade	Timing for Restarting Treatment	Discontinue Subject
Diarrhea/Colitis	2-3	Toxicity resolves to Grade 0-1.	Toxicity does not resolve within 12 weeks of last dose or inability to reduce corticosteroid to 10 mg or less of prednisone or equivalent per day within 12 weeks.
	4	Permanently discontinue	Permanently discontinue
AST, ALT, or Increased Bilirubin	2	Toxicity resolves to Grade 0-1	Toxicity does not resolve within 12 weeks of last dose.
	3-4	Permanently discontinue (see exception below) 	Permanently discontinue
Type 1 diabetes mellitus (if new onset) or Hyperglycemia	T1DM or 3-4	Hold pembrolizumab for new onset Type 1 diabetes mellitus or Grade 3-4 hyperglycemia associated with evidence of beta cell failure.	Resume pembrolizumab when patients are clinically and metabolically stable.
Hypophysitis	2-3	Toxicity resolves to Grade 0-1	Toxicity does not resolve within 12 weeks of last dose or inability to reduce corticosteroid to 10 mg or less of prednisone or equivalent per day within 12 weeks.
	4	Permanently discontinue	Permanently discontinue

*CONFIDENTIAL*

*This document is confidential. Do not disclose or use unless authorized.*

Toxicity	Hold Treatment For Grade	Timing for Restarting Treatment	Discontinue Subject
Hyperthyroidism	3	Toxicity resolves to Grade 0-1	Toxicity does not resolve within 12 weeks of last dose or inability to reduce corticosteroid to 10 mg or less of prednisone or equivalent per day within 12 weeks.
	4	Permanently discontinue	Permanently discontinue
Hypothyroidism	2-4	Therapy with pembrolizumab can be continued while treatment for the thyroid disorder is instituted	Therapy with pembrolizumab can be continued while treatment for the thyroid disorder is instituted.
Infusion Reaction	3-4	Permanently discontinue	Permanently discontinue

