**Note: Permanently discontinue for any severe or Grade 3 drug-related AE that recurs or any life-threatening event.**

 For patients with liver metastasis who begin treatment with Grade 2 AST or ALT, if AST or ALT increases by greater than or equal to 50% relative to baseline and lasts for at least 1 week then patients should be discontinued.

 Patients with intolerable or persistent Grade 2 drug-related AE may hold study medication at physician discretion. Permanently discontinue study drug for persistent Grade 2 adverse reactions for which treatment with study drug has been held, that do not recover to Grade 0-1 within 12 weeks of the last dose.

Dosing interruptions are permitted in the case of medical / surgical events or logistical reasons not related to study therapy (e.g., elective surgery, unrelated medical events, patient vacation, and/or holidays). Subjects should be placed back on study therapy within 3 weeks of the scheduled interruption, unless otherwise discussed with the Sponsor. The reason for interruption should be documented in the patient's study record.

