### 7.1.2 Timing of Dose Administration

Trial treatment should be administered on Day 1 of each cycle after all procedures/assessments have been completed as detailed on the Trial Flow Chart (Section 9.0). Trial treatment may be administered up to 3 days before or after the scheduled Day 1 of each cycle due to administrative or other reasons.

All trial treatments will typically be administered on an outpatient basis.

Pembrolizumab up to 200 mg will be administered as a 30 minute IV infusion every 3 weeks. Sites should make every effort to target infusion timing to be as close to 30 minutes as possible. However, given the variability of infusion pumps from site to site, a window of -5 minutes and +10 minutes is permitted (i.e., infusion time is 30 minutes: -5 min/+10 min). Pembrolizumab will be administered after the operative endoscopy. If the patient is found to have progressive disease by endoscopic evaluation, the patient will continue to receive pembrolizumab until the next in-office clinical examination in 3 weeks which confirms progressive disease of the target lesion.

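### Sections 7.1.1.2, 7.7 and 10.1.1.11 give rules that do not agree on when a patient held for toxicity must come off pembrolizumab

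*Combined protocol and SAP*

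**What the plan says.** **Section 7.7** lists removal criteria and makes them binding: "Participants will be removed from the protocol therapy when any of these criteria apply". One criterion is "Treatment was held for 9 weeks for reasons other than complete response". No start date is given for the hold, and complete response is the only exception. A separate criterion in the same list is "Unacceptable adverse experiences as described in Section 7.1.1", which brings in the dose-modification rules.

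**Section 7.1.1.2, Table 3** has seven graded rows that allow a hold and a restart: diarrhea/colitis, hepatic, hypophysitis, hyperthyroidism, pneumonitis, renal, and all other drug-related toxicity. In each, one ground for discontinuing is "Toxicity does not resolve within 12 weeks of last dose". Every one of these rows except the hepatic row adds a second ground: "inability to reduce corticosteroid to 10 mg or less of prednisone or equivalent per day within 12 weeks". Footnote 2, on persistent Grade 2 events, discontinues those "that do not recover to Grade 0-1 within 12 weeks of the last dose".

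The row for new-onset type 1 diabetes or Grade 3-4 hyperglycemia is different. Its entry in the column headed Discontinue Subject reads "Resume pembrolizumab when patients are clinically and metabolically stable", and no duration appears anywhere in the row.

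**Section 10.1.1.11**, on trial compliance, says that a departure from the treatment plan caused by toxicity leads to the patient coming off treatment. It allows no exception and does not refer to Table 3.

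**Section 7.1.2** sets the schedule: "Pembrolizumab up to 200 mg will be administered as a 30 minute IV infusion every 3 weeks".

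**Sections 2.1 and 7.1.4** stop the study if more than 30% of patients discontinue pembrolizumab because of an adverse event.

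**The concern.** A patient on hold for toxicity comes under up to three rules. Section 7.7 gives 9 weeks with no start date. Table 3 gives 12 weeks from the last dose, or no limit for diabetes/hyperglycemia. Section 10.1.1.11 allows no interruption at all. No order of precedence is stated, and Section 7.7 makes both its own limit and the Section 7.1.1 rules grounds for removal. In a multi-center trial, two sites could each follow the text and reach opposite decisions on the same patient.

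What is at stake is mainly who stays on drug. Next is the count for the 30% stopping rule. Because Section 7.7 lists the 9-week hold separately from adverse-event removal, it is also unclear whether a removal under the 9-week criterion counts as a discontinuation due to an adverse event.

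**Working it through.** The plan gives no figure of its own to reproduce here. The check is timeline arithmetic plus a comparison of the passages.

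**(a) The 9-week and 12-week limits.** Inputs: dosing interval 3 weeks (Section 7.1.2), hold limit 9 weeks (Section 7.7), toxicity limit 12 weeks from the last dose (Table 3 and footnote 2). Let *s* be the week after the last dose at which the hold clock starts. The documents do not give *s*, so I assume a range of 0 to 3 weeks.

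Removal under Section 7.7 falls at week *s* + 9 after the last dose. The gap to Table 3 is 12 − (*s* + 9) = 3 − *s*.

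| Hold clock starts (weeks after last dose) | Section 7.7 removal (week) | Table 3 limit (week) | Gap (weeks) |
|---|---|---|---|
| 0 | 9 | 12 | 3 |
| 1 | 10 | 12 | 2 |
| 2 | 11 | 12 | 1 |
| 3 (first missed dose) | 12 | 12 | 0 |

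Counted from the first missed dose, the limits coincide. What remains on that reading is the boundary: a restart on the 3-week grid at week 12 is exactly 9 weeks held. The ±3-day dosing window in Section 7.1.2 moves the Section 7.7 limit to between (21 − 3)/7 + 9 = 11.6 and (21 + 3)/7 + 9 = 12.4 weeks.

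Table 3's corticosteroid limit has no start point. If it runs from the start of steroids, and that is 0 to 3 weeks after the last dose (assumption), it ends at week 12 to 15. At the upper end it lies 3 weeks beyond the Section 7.7 limit, even when the hold is counted from the first missed dose.

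**(b) Diabetes/hyperglycemia.** Take a patient who becomes stable after more than 9 weeks of hold, from whatever date the hold is counted. Table 3 says to resume. Section 7.7 says to remove, because the hold was not for complete response. Both conditions are met on every clock.

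**(c) Section 10.1.1.11.** Take a patient with Grade 2 pneumonitis that resolves to Grade 0-1 at week 5, with steroids already reduced as required. Table 3 allows restart, and the 9-week limit has not been reached. Section 10.1.1.11 takes the patient off treatment because an interruption occurred. The same holds for each of the seven graded hold-and-restart rows and for the diabetes/hyperglycemia row.

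**Stopping rule.** The smallest count above 30% of *N* is floor(0.30 × *N*) + 1. Section 14.1 gives 21 evaluable adults, 22 adults entered, and about 2–3 pediatric patients in addition, so *N* is 24–25 if they are included.

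| *N* | 0.30 × *N* | Count that crosses 30% | One fewer |
|---|---|---|---|
| 21 | 6.3 | 7 (33.3%) | 6 (28.6%) |
| 22 | 6.6 | 7 (31.8%) | 6 (27.3%) |
| 24 | 7.2 | 8 (33.3%) | 7 (29.2%) |
| 25 | 7.5 | 8 (32.0%) | 7 (28.0%) |

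The rule refers to patients without stating the denominator.

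**The case against.** The best defense is that 9 and 12 weeks are one limit written two ways. On a 3-weekly schedule nothing is withheld until a dose falls due, so the first missed dose is the natural start of a hold, and 3 + 9 = 12. The paragraph after footnote 2 gives some support, since it measures non-toxicity interruptions from the scheduled interruption and not from the last dose. This largely stands. A reader might infer a flat contradiction between the two numbers, but the documents do not support that, because the numbers need not share an origin. The undefined start, the week-12 boundary and the unanchored steroid limit remain.

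Second, the Section 7.7 criteria are cumulative, so a Table 3 row with no limit could simply fall under the 9-week cap. That is a fair reading, and a reader should not take the diabetes/hyperglycemia row as permission for an unlimited hold: the row is silent on duration. But the text never calls Section 7.7 an outer cap, and the row's only instruction is to resume.

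Third, a reader might infer that early removal damages the primary response rate. The documents do not support this as a direct effect. Section 14.1 keeps every eligible adult who begins treatment in the efficacy population, and Section 7.9 counts drug-related discontinuations without replacement. The flow chart calls for imaging and/or endoscopy at discontinuation without confirmed progression. Section 10.1.5.4 continues clinical examination every 8 weeks and imaging every 6 months. What changes is that examinations go from 3-weekly to 8-weekly and no further drug is given.

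Finally, one patient can decide any threshold, and the documents give no estimate of how many would recover within a disputed window. Both points are right, so the effect on the stopping rule is possible but not quantified.

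None of these arguments answers Section 10.1.1.11.

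**Conclusion.** The hold, restart and removal rules do not agree and must be reconciled.

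- The 9-week and 12-week limits differ by 0 to 3 weeks, depending on an undefined start. They coincide if the clock starts at the first missed dose.
- The diabetes/hyperglycemia row and Section 7.7 give different instructions for a patient stable only after 9 weeks of hold, unless the row is read as subject to the cap, which the text does not state.
- Section 10.1.1.11 contradicts Table 3's hold-and-restart rows outright, on any clock.

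The consequence is uncertainty about who stays on drug and possibly about the 30% count, which is crossed at 7 of 21–22 adults or 8 of 24–25 patients if pediatric patients are included. It would go too far to take 7 of 21 as the trigger, because the denominator is not stated. The effect on the response rate is indirect. These conclusions rest on the assumed 0-to-3-week range for the start of a hold and of steroid treatment. They take no view on which limit is right.

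**What to change.** Reconcile Section 7.1.1.2 (Table 3 and footnote 2), Section 7.7 and Section 10.1.1.11:

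- Define when a hold starts and use one clock in all three places, including what applies at exactly the limit.
- Give the 12-week corticosteroid limit a start point.
- State whether the type 1 diabetes/hyperglycemia row falls under the Section 7.7 limit, and check that its resume instruction sits in the intended column.
- Revise either Section 10.1.1.11 or Table 3 so that they no longer contradict each other.
- In Sections 2.1 and 7.1.4, state the denominator of the 30% rule and whether a removal under the 9-week criterion counts toward it when the hold was for toxicity.

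The limits themselves are for the sponsor to choose. The cost is wording in these sections, submitted as an amendment for IRB approval as Section 13.1 requires. The sample size and the two-stage design do not change.
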